6.2.4 Post Intervention Measures (Day 0)

Immediately following the study physician visit, subjects who consented to blood draws will be asked to have another 7.5mL sample of blood taken (to obtain RNA and plasma) and all subjects will be asked to complete the following questionnaires:

- CARE – Consultation And Relational Empathy questionnaire, a validated and commonly used 10 item measure for assessing the quality of the patient encounter and perceptions of empathy from the treatment provider [76]. I used it in my pilot study.
- HEAL Patient-Provider Connection – a subset of the Healing Encounters and Attitudes List, a recently validated 7-item measure of the patient-provider connection. This is a patient-reported outcome developed as part of a set of tools to measure non-specific factors in treatment using the NIH PROMIS methodology [77].
- Current Stress Question – 1 item self-report measure of current stress level on a scale of 0 (no stress) to 10 (extreme stress).

6.2.5 Telephone check-in

Study coordinators will call enrolled subjects who have completed study visit 1 approximately half-way between the first and second study visits. These telephone check-ins will a) serve as a reminder to participants to complete their daily symptom diary, b) address any participant questions or concerns, and c) remind/confirm participants' second study visit appointment.

6.2.6 Completion/Final Evaluation

We will attempt to schedule subjects' Visit 2 appointments as close to the 2 week window as possible, but will allow a window of 13-18 days. Visit 2 will be scheduled simultaneously with Visit 1 to help promote adherence to this timeline.

- Current medication List – will be pulled from Epic or the prior visit and verified with the subject by a study team physician.
- Blood draw (optional) – 7.5mL of blood will be obtained by a research nurse in the CRC or other appropriate clinician. Blood will be processed to obtain RNA, and plasma then frozen at -80°C for later omics analyses
- GERD-HRQL - a validated 11 item scale for assessing the impact of GERD symptoms on health-related quality of life [70].
- NIH PROMIS GERD scale – a validated 13 item instrument assessing frequency and severity of GERD symptoms over a 7 day recall period [26].
- GSRS: The Gastrointestinal Symptom Rating Scale is a validated 15 item instrument for measuring the severity of gastrointestinal symptoms [71]. It contains 5 subscales: abdominal pain, reflux syndrome, diarrhea syndrome, indigestion syndrome, and constipation syndrome.
- Current Stress Question – 1 item self-report measure of current stress level on a scale of 0 (no stress) to 10 (extreme stress).
- Perceived Stress Scale (PSS) – a widely used 10 item measure of perceived stress that has been shown to correlate with a variety of different health outcomes [72].
- Adverse events – study staff will ask subjects if they experienced any adverse events and ask about any hospital or emergency room visits since enrollment.
- Daily symptom diary – Identical in content to the baseline symptom diary, this 14 day diary allows subjects to track the frequency and severity of 9 different GERD and dyspepsia-related symptoms on a 5 point scale as well as any medications, supplements, or other products used to help manage symptoms.
- Qualitative interview – a study team member will conduct a semi-structured qualitative interview (see Appendix F) with each subject after the subject has completed questionnaires and prior to the debriefing. These interviews will be audio recorded and will include questions about their perceptions of their interaction with the study provider and with healthcare providers in general and their experience participating in the study.
- GERD handout – an informational handout on GERD and possible treatment approaches will be provided to subjects. See Appendix I.
- Debriefing – a study team physician will debrief with each subject regarding the actual nature of the study. See Appendix G for a debriefing script.

7. SAFETY ASSESSMENTS

Expected risks to subjects are as follows:

- Study questionnaires: Symptom and behavioral data collection involves virtually no risk; however, psychosocial tests or questions about symptom intensity may cause minor emotional distress. Because participants are free to stop at any time and will be reminded of this throughout the assessment process, the risk of distress is low. In our experience, such questionnaires are well tolerated and complications are extremely rare.
- Discomfort from ECG/GSR leads and physiologic monitoring: Some participants may experience minor skin irritation due to the adhesive used to apply leads for physiologic monitoring. Subjects with known adhesive allergies will not be eligible to participate in the study. Some participants may experience psychological distress knowing that their physiology is being monitored. The physiologic monitoring will be described in the consent document and care will be taken to minimize such distress. Participants will be free to stop at any time. In general, such monitoring is well-tolerated.
- Discomfort from blood draws: some participants may have an aversion to needles, blood, and/or the drawing of blood. Blood will be drawn by experienced nurses at the MGH CRC and care will be taken to minimize discomfort to participants. Blood draws are generally well-tolerated, although occasionally there may be bruising or discomfort at the site. Rarely an infection can occur. The blood draw will be an optional component of the study, and if an enrolled subject consents to the blood draw and is particularly challenging to draw blood from, we will not require a successful blood draw to be a condition of continued enrollment in the study.
- Videotaping: Some participants may experience psychological distress knowing that they are being videotaped. Participants will be free to stop at any time. In general, videotaping is generally well-tolerated.
- Deception: Subjects may experience minor psychological distress at study visit 2 when they learn that some information was withheld from them at enrollment. Based upon our experience with our prior study, we feel this is unlikely to happen or to be problematic as we have experience conducting such debriefings and subjects generally understand why such information was withheld initially.

7.1 Specification of Safety Parameters

Blood will be drawn by experienced nursing staff and samples will be processed then frozen for later analysis. There will be no immediate laboratory analysis of the samples collected.

7.2 Methods and Timing for Assessing, Recording, and Analyzing Safety Parameters

When subjects return for their follow-up visit, a study team member will inquire about any changes to their health or medical visits (including emergency room visits or hospitalizations) since their initial study visit. We do not anticipate any issues that will be causally related to the study. If a subject reports a new or worsening symptom that is medically concerning (e.g., bright red blood per rectum), they will be referred to their

Tool Revision History

Version: 11.0

Version Date: 5.8.2020

usual healthcare provider for further evaluation.

7.3 Adverse Events and Serious Adverse Events

An **adverse event (AE)** is any unfavorable or unintended diagnosis, symptom, sign, syndrome or disease which either occurs during the study (having been absent at baseline), or if present at baseline, appears to worsen.

A **serious adverse event (SAE)** is any untoward medical occurrence that results in death, is life threatening, requires inpatient hospitalization or prolongation of existing hospitalization, results in persistent or significant disability/incapacity, or is a congenital anomaly.

During the follow-up visit, the study team member will specifically ask about any new or worsening symptoms in the last 2 weeks, unanticipated medical appointments, emergency room, or hospital visits.

In addition, during telephone check-ins, the study research coordinator will record any health concerns reported by subjects (not specifically solicited) and report these to the study PI. If there are any signs or symptoms of concern or that require further clarification, the study PI will contact the subject.

- Unexpected fatal or life-threatening AEs related to the intervention will be reported to the National Center for Complementary and Integrative Health (NCCIH) Program Officer, Independent Safety Monitor(s), and Partner's IRB within 3 business days of the investigator becoming aware of the event. Other serious and unexpected AEs related to the intervention will be reported within 5 business days.
- Anticipated or unrelated SAEs will be handled in a less urgent manner but will be reported to the Independent Safety Monitor(s), IRB, and other oversight organizations in accordance with their requirements and will be reported to NCCIH on an annual basis.
- All other AEs documented during the course of the trial will be reported to NCCIH and the Partner's IRB on an annual basis by way of inclusion in the annual report and in the annual AE summary which will be provided to NCCIH and to the Independent Monitors. The Independent Safety Monitor(s) Report will state that all AEs have been reviewed (see Data Safety and Monitoring Plan).

7.4 Reporting Procedures

Study staff and visit intervention providers will be instructed to report all adverse events (or potential AEs) to the study PI ([name]). Determination of relatedness will be made in conjunction with [name] and/or [name]. An electronic log of various types of AEs will be kept and updated by study staff, including the PI.

7.5 Follow-up for Adverse Events

AEs will be followed-up by the study PI by phone calls to the subject and/or monitoring of the medical record until they are resolved or considered stable. Formal AE follow-up will end with subjects' follow-up visit unless they have an ongoing issue or call to report

Tool Revision History

Version: 11.0

Version Date: 5.8.2020

an event after completing the study.

7.6 Safety Monitoring

Please see the separate data safety and monitoring plan for this study, found in Appendix H.

8. INTERVENTION DISCONTINUATION

We will discontinue the intervention for any subject who declines or is unable to complete the study questionnaires, physiologic monitoring, and/or video recording. Any subjects who are disruptive or felt to pose a threat to study staff will also be discontinued. Given the nature of the study intervention and outcomes, we will not continue to follow subjects who discontinue the study, unless it is for a health-related reason to monitor an adverse event.

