6.2.3 Blinding

This is a single-blinded study. Subjects will be unaware of the possibility for two different types of study visits. Study providers and staff will be aware of the study intervention delivered, but only immediately prior to the study visit to decrease the potential for introducing bias in how study staff interact with subjects during recruitment and consent. Subjects will be debriefed at the end of the Visit 2 regarding the nature of the study and the intervention that they received. Data will be analyzed in a blinded fashion, also to avoid introducing bias. Given the low-risk nature of the study, we do not anticipate a need to break the blind while a subject is enrolled.

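### Subjects who stop between consent and Visit 2 have no stated exit adverse-event inquiry and no stated debriefing

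*Combined protocol and SAP*

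**What the plan says.** **Leaving the study.** Section 8 gives the trigger: "We will discontinue the intervention for any subject who declines or is unable to complete the study questionnaires, physiologic monitoring, and/or video recording". It then says of those who leave that "we will not continue to follow subjects who discontinue the study, unless it is for a health-related reason to monitor an adverse event".

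**Expected reasons to leave.** Section 7 lists distress from questionnaires, physiologic monitoring and videotaping among the expected risks, and for each it notes that the subject may stop. On questionnaires it reasons "Because participants are free to stop at any time"; on video it says "Some participants may experience psychological distress knowing that they are being videotaped. Participants will be free to stop at any time".

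**Asking about harm.** Section 7.3 places the direct questions at Visit 2: "During the follow-up visit, the study team member will specifically ask about any new or worsening symptoms in the last 2 weeks". Section 6.2.6 agrees: at that visit "study staff will ask subjects if they experienced any adverse events and ask about any hospital or emergency room visits since enrollment". The mid-study call works differently: "the study research coordinator will record any health concerns reported by subjects (not specifically solicited) and report these to the study PI".

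**Debriefing.** Section 6.2.3 states that "Subjects will be debriefed at the end of the Visit 2 regarding the nature of the study". Sections 4.3, 5.2 and 9.2 and the schedule in section 6.1 give the same timing.

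**The concern.** The procedures whose refusal leads to discontinuation (questionnaires, monitoring, video) are the same ones that section 7 names as possible sources of distress. A subject who finds one of them upsetting and stops is thus moved out of follow-up before the scheduled point at which anyone asks about harm.

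Two things are at stake. The first is safety ascertainment: solicited AE data come only from people who reach Visit 2, and those who stopped early may differ from them in this very respect. The second is disclosure. Subjects enrol under altered consent, without being told that the patient-provider interaction is under study or that there are two visit types. Section 5.2 describes the later disclosure as part of the plan it believes meets the criteria for altering consent. As written, that disclosure does not reach anyone who leaves before Visit 2.

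**Working it through.** No arithmetic applies, and the plan gives no figure to reproduce. The check is to set the sections side by side and follow an early leaver through them.

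1. **Follow-up after discontinuation (section 8).** It stops, with one exception: monitoring an AE for a health-related reason. The exception presupposes that somebody already knows of an event. Debriefing is not mentioned.
2. **Solicited AE questions.** The schedule in section 6.1 marks adverse events under Visit 2 only. Sections 6.2.6, 7.2 and 7.3 place the questions at the same visit. No section places them at exit.
3. **Other AE routes.** Section 6.2.5 provides a check-in call to those who completed Visit 1. By section 7.3, that call records only what the subject volunteers. Section 7.4 has staff and visit providers pass actual or potential AEs to the principal investigator, with no limit to Visit 2. Section 7.5 has the investigator follow known events by telephone or through the medical record.
4. **Debriefing.** Sections 4.3, 5.2, 6.1, 6.2.3, 6.2.6 and 9.2 all place it at the second visit. No section gives an earlier or alternative occasion.

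Applying these rules to four kinds of subject:

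| Subject | Asked directly about AEs? | AE captured another way? | Debriefed? |
|---|---|---|---|
| Attends Visit 2 | Yes | Yes | Yes |
| Stops early; distress noticed or volunteered | Not stated | Yes (7.3 to 7.5; section 8 exception) | Not stated |
| Stops early; distress neither noticed nor volunteered | Not stated | No | Not stated |
| Stops early; no AE | Not stated | Not applicable | Not stated |

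The AE gap is the third row only. The debriefing gap covers all three early-leaver rows.

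**Size.** The number of subjects exposed is the number enrolled minus the number attending Visit 2. Section 3 enrols until 24 subjects complete, and the plan gives no dropout rate, so this difference is unknown. The plan does expect that it may not be zero: section 9.2 allows the randomization to be rebalanced within a stratum if a subject drops out.

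**The case against.** The strongest case on the other side has five parts.

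- **Distressed leavers are not simply lost.** A reader might infer that people who stop because of distress are never asked about harm. The documents do not support that absolute. Section 8 keeps follow-up where there is an AE to monitor, the AE definition in section 7.3 is wide enough to include distress, and section 7.4 binds staff and providers throughout. Monitoring and video take place only at Visit 1, so a subject who stops because of them does so on site, among people with that reporting duty. This stands, and it limits the AE gap to events that nobody recognises or mentions.
- **The AE report is not restricted to completers.** A reader might infer that the monitors see a completers-only figure. Section 7.3 instead sends all AEs documented during the trial to the annual summary and sets no completer denominator. This also stands; only the solicited data are confined to Visit 2 attenders.
- **Few subjects may be affected.** Willingness to be videotaped and monitored is an inclusion criterion, which should make such stops uncommon. That is reasonable, but with no dropout rate it can be neither confirmed nor turned into a number.
- **The appendices may deal with it.** Appendix G (debriefing script) and Appendix H (safety monitoring plan) are listed but could not be read. Either might cover early leavers. If so, the remaining problem is that section 8 points the other way without referring to them.
- **Altered consent does not rest on debriefing alone.** Section 4.3 argues from minimal risk. A subject who stops at the baseline questionnaires, before randomization as section 6.2.2 orders it, has received neither visit type. This weakens any claim that the consent justification fails. It does not supply a debriefing: the purpose and the existence of two visit types were still withheld from that subject.

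**Conclusion.** The point holds as a gap between sections. Section 8 closes follow-up for early leavers, while the solicited AE questions and the debriefing exist only at Visit 2. A team following the text exactly would neither ask a departing subject about harm, unless an event was already known, nor tell that subject what was concealed.

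The debriefing part is the firmer of the two, because nothing in the text available offsets it. The AE part is confined to unrecognised and unvolunteered events. Any resulting error in the AE summary would be toward under-reporting, but its size cannot be estimated from the documents. No primary or secondary analysis is affected.

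The conclusion assumes that Appendices G and H do not already provide for early leavers.

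**What to change.** Reconcile sections 5.2, 6.2.3, 7.3 and 8 by amending the last sentence of section 8. Possible wording:

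> Subjects who discontinue after consent will be offered the adverse-event questions of section 7.3 and the debriefing in Appendix G, at the time they leave or in one telephone call. They may decline either. No other follow-up will take place unless an adverse event needs monitoring.

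Add a matching line to sections 5.2 and 6.2.3 on the timing of debriefing, and to section 7.3 on the timing of the AE questions. Ask the AE questions before the debriefing, so that the disclosure does not colour the answers. State in section 7.3 that AEs are reported for all enrolled subjects, with completers and non-completers shown separately.

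If Appendix G or H already provides for early leavers, a cross-reference from section 8 covers that part.

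The cost is a short amendment and one extra contact per leaver, made by existing staff with the existing questions and script. Some leavers will decline, so ascertainment and disclosure will still be incomplete. Recording who was offered the contact and who declined would make that visible.

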9. STATISTICAL CONSIDERATIONS

9.1 General Design Issues

Design: This is a pilot, proof-of-concept, single-blinded randomized controlled trial in which subjects will be randomized in a 2:1 fashion to receive either an expanded or standard visit intervention. We are including both types of visit interventions and randomizing subjects in this way to maximize our potential to measure a wide range in physiologic concordance within the patient-provider dyads so we can best assess our hypotheses.

Primary hypotheses:

1. Subjects in patient-provider dyads with higher levels of concordance in GSR or HRV (i.e., where patient and provider GSR or HRV change in concert) will demonstrate greater improvement in GERD symptom severity than subjects in patient-provider dyads with lower levels of concordance in these measures.
2. Subjects who experience physiologic changes similar to those elicited by mind-body techniques (i.e., decreased GSR and increased high frequency HRV) over the course of their visit will demonstrate greater improvements in GERD symptom severity than subjects who do not.

Secondary hypothesis:

1. As the expanded visit unfolds, providers will demonstrate significantly more patient-centered, nonverbally supportive behaviors and have higher global impression ratings of rapport, engagement, and reciprocity compared to early in the expanded visit and both early and late in the standard visit.

Primary outcomes:

1. Correlation between physiologic synchrony in patient-provider dyads (GSR or HRV) and subsequent improvement in GERD symptom severity.
2. Correlation between absolute changes in GSR within subjects over the course of the study visit and subsequent changes in GERD symptom severity.

Tool Revision History

Version: 11.0

Version Date: 5.8.2020

3. Correlation between absolute changes in high frequency HRV within subjects over the course of the study visit and subsequent changes in GERD symptom severity.

Secondary outcomes:

1. The difference in the frequency of supportive provider behaviors between the standard and expanded visit groups.
2. The difference in the ratings of rapport, engagement, and reciprocity between the standard and expanded visit groups.

Validity and reliability of outcome measures:

1. Assessment of physiologic concordance has been described by a number of groups and we will be using similar methodology [42,78].
2. GERD symptom severity will be assessed by a daily symptom diary used by a number of other groups in medication trials and in our previous study [61,79,80]. The average daily GERD symptom severity is based on the daily sum of scores from the first three questions assessing severity of daytime heartburn, nighttime heartburn, and acid reflux averaged over a 7 day period. The change in GERD symptom severity is calculated by subtracting the average daily GERD symptom severity score during the last 7 days of the study from the average daily GERD symptom severity score at study enrollment. The other GERD symptom questionnaires we are using have also been validated [26,70,71].
3. Social psychologists have developed and validated a variety of coding schemes to analyze providers' verbal and non-verbal behaviors and to link these behaviors with patient satisfaction, understanding, trust, rapport, empathy, and a variety of related factors [9,55–60]. We will use a subset of these validated coding schemes. Thin slices have shown high reliability and validity for behaviors such as gaze, nods, and smiles [81].

9.2 Sample Size and Randomization

This is a pilot study whose aim is to identify features on which to focus in subsequent studies. For the primary outcome, we would consider an observed correlation greater than $r = 0.20$ adequate evidence of a positive association worthy of further investigation. With a sample size of 24 patient-provider dyads, the study will have an 80% probability of obtaining an estimated correlation between physiologic concordance and changes in GERD symptoms (our primary outcome) greater than $r = 0.20$ if the true correlation is at least $\rho = 0.36$. The study will have 80% power to declare the correlation significantly greater than zero based on a two-sided $\alpha = 0.05$ if the true correlation is at least $\rho = 0.54$.

Treatment Assignment Procedures

A randomization scheme will be devised before the start of the study by the study biostatistician who will retain the code and will be responsible for breaking the blind at the end of the study. We do not anticipate a need to break the blind during the study because

Tool Revision History

Version: 11.0

Version Date: 5.8.2020

we are not expecting serious adverse events to occur more frequently in one visit group than another. Randomization will be stratified by provider, with a goal to have 4 providers each see 6 subjects (4 expanded and 2 standard visits each). If a provider cannot commit to this many visits, the study biostatistician may need to adjust the randomization scheme.

The study biostatistician will create numbered envelopes that will indicate which intervention is to be delivered. After a subject has consented to participate in the study, while he or she is completing the baseline questionnaires, immediately prior to the actual visit intervention, the envelope corresponding to the enrolled subject will be opened to reveal which intervention is to be delivered.

If a subject drops or is unable to complete the study, the statistician may need to rebalance the randomization scheme within a stratum.

Subjects will be informed of their “treatment” assignment during a debriefing at the end of the second study visit.

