3. STUDY DESIGN

Study design: Single-center, single-blind, pilot randomized controlled trial

Primary outcomes:

- 1) Correlation between physiologic synchrony in patient-provider dyads (GSR or HRV) and improvement in GERD symptom severity.
- 2) Correlation between absolute changes in GSR within subjects over the course of the study visit and subsequent changes in GERD symptom severity.
- 3) Correlation between absolute changes in high frequency HRV within subjects over the course of the study visit and subsequent changes in GERD symptom severity.

Secondary outcomes:

- 1) The difference in the frequency of supportive provider behaviors between the standard and expanded visit groups.
- 2) The difference in the ratings of rapport, engagement, and reciprocity between the standard and expanded visit groups.

Study population:

Men and women age 21-70 with heartburn symptoms 3 or more days per week. We will enroll until we reach 24 completing subjects.

Study location:

The Clinical Research Center (CRC) at Massachusetts General Hospital (MGH), the Benson-Henry Institute (BHI) for Mind Body Medicine, or another MGH location.

Length of subject participation: 2 weeks

Length of study enrollment: 12-14 months

Groups:

- 1) Standard visit (n=8), modeled after an empathic, high quality conventional primary care visit.
- 2) Expanded visit (n=16), modeled after a visit with an integrative medicine provider

Randomization:

The randomization code will be generated by the study statistician as described below (section 4.3). The study will be single-blinded (study providers and the research team will know what the subject is receiving but the subject will not). Randomization will be

Tool Revision History

Version: 11.0

Version Date: 5.8.2020

stratified based on study provider. We anticipate 4 providers each seeing 6 subjects (2 standard visits, 4 expanded visits).

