9.5.1 Primary Outcomes

1. Pearson correlation between concordance in GSR or HRV within patient-provider dyads and improvement in GERD symptom severity in the patient. Changes in GERD symptom severity will be calculated from the GERD symptom diaries collected at the first and second study visits. HRV and GSR will be measured during the visit intervention (first study visit).

We will calculate Pearson correlations between the slopes of time-locked patient and provider GSR data in 15 second intervals after smoothing. An index of concordance in GSR responses for each patient-provider dyad will be calculated as the natural logarithm of the sum of the positive correlations from the entire session minus the natural logarithm of the sum of the absolute value of negative correlations across the session [78]. Dyads with a more positive index demonstrate greater concordance, and the subjects in these dyads would be expected to demonstrate greater improvement in GERD symptom severity.

I will also perform an analysis using a similar approach to analyze the HRV data – comparing variation in the beat-to-beat intervals over short segments of time and calculating Pearson correlation coefficients for time-locked patient and provider data for these intervals.

2. Correlation between change in GSR (or high frequency HRV) and subsequent changes in GERD symptoms. We will calculate absolute changes in GSR, and also for high frequency HRV, within study subjects from the beginning to the end of the study visit and determine the Pearson correlation between these changes and reported changes in GERD symptom severity. As a secondary analysis, I will test whether changes in GSR and HRV are a function of baseline perceived stress and if that relationship differs between the standard and expanded visit interventions.

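### Does Section 9.2 need to say whether the r > 0.20 screen applies to GSR and HRV concordance separately or is met by either?

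*Combined protocol and SAP*

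**What the plan says.** Section 9.2 treats the study as a pilot meant to pick out features for later work. It would regard "an observed correlation greater than $r = 0.20$ adequate evidence of a positive association worthy of further investigation". It then gives two operating figures for 24 dyads, both in the singular. The first is an 80% chance of obtaining a "correlation between physiologic concordance and changes in GERD symptoms (our primary outcome) greater than" 0.20 when the true correlation is 0.36. The second is 80% power for a two-sided 5% test when the true correlation is 0.54.

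The outcome behind that single correlation involves two measures. Section 3 lists it as "Correlation between physiologic synchrony in patient-provider dyads (GSR or HRV) and improvement in GERD symptom severity". Section 9.1 repeats it almost word for word, and its first hypothesis concerns "Subjects in patient-provider dyads with higher levels of concordance in GSR or HRV". Section 9.5.1 defines the analysis as a "Pearson correlation between concordance in GSR or HRV within patient-provider dyads and improvement in GERD symptom severity in the patient". It builds a GSR concordance index for each dyad and then adds: "I will also perform an analysis using a similar approach to analyze the HRV data". No score combining GSR and HRV is defined, and neither measure is named as the lead.

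**The concern.** A rule written for one correlation will meet two. Read index by index, each correlation stands or falls against 0.20 on its own. Read as a single outcome that either measure can satisfy, concordance as a whole passes when the larger of the two correlations exceeds 0.20. The wording gives some support to the second reading: the within-subject changes in GSR and in high frequency HRV are listed as two numbered outcomes in Sections 3 and 9.1, whereas concordance in the two measures stays one numbered outcome and one hypothesis.

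The readings differ in how easily the screen is passed by chance, and the 80% in Section 9.2 describes only the first. If exactly one index passed, someone could choose after seeing the data whether to say that concordance had passed or only that index. Since the purpose of the pilot is to decide what to carry forward, that would be a loose end in the rule that serves its purpose.

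**Working it through.** **Inputs.** From Section 9.2: n = 24, threshold r > 0.20, true correlations 0.36 and 0.54, two-sided alpha 0.05. From Sections 9.1 and 9.5.1: change is the enrolment score minus the final score, so improvement is positive and the screen is one-sided. The correlation between the two concordance indices, c, is not in the documents; values from 0 to 0.9 are assumed.

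**Step 1: the plan's own figures, one index.** Fisher's z has standard error 1/√(24 − 3) = 0.218.

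- True correlation 0.36: (atanh 0.36 − atanh 0.20) × √21 = (0.3769 − 0.2027) × 4.583 = 0.798, giving 78.8%. Adding the bias term 0.36/(2 × 23) gives 79.8%. Simulation gives 80.0%. The stated 80% is reproduced.
- True correlation 0.54: the two-sided 5% critical value is |r| = 0.404. Fisher's z with the bias term gives 80.4%; simulation gives 80.8%. The stated 80% is reproduced.

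**Step 2: pass rate of one index with no association.** t = 0.20 × √22 / √(1 − 0.04) = 0.957 on 22 degrees of freedom, so P(r > 0.20) = 17.4%.

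**Step 3: pass rate if either index suffices, no association.** For independent indices, 1 − (1 − 0.1744)² = 31.8%. For correlated indices (400,000 simulated trials per setting, trivariate normal):

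| Assumed c | At least one passes | Both pass | Exactly one passes |
|---|---|---|---|
| 0 | 31.8% | 3.0% | 28.8% |
| 0.3 | 29.6% | 5.3% | 24.4% |
| 0.5 | 27.9% | 7.2% | 20.7% |
| 0.7 | 25.4% | 9.4% | 16.0% |
| 0.9 | 22.1% | 12.9% | 9.2% |

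The last column is the difference of the two before it, taken before rounding. It is the share of null studies in which the two readings could lead to different statements.

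**Step 4: how much weight the screen can bear.** At an observed r of exactly 0.20, the 95% interval is tanh(0.2027 ± 1.96/4.583) = tanh(−0.225) to tanh(0.630), or about −0.22 to 0.56. On either reading, passing is a weak signal that would be reported with its estimate.

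**Step 5: which reading the text supports.**

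- Section 9.2 speaks of features in the plural and of an observed correlation. A screen for features is naturally applied feature by feature.
- Section 9.5.1 gives GSR its own index and HRV a further analysis. With no composite, every observed correlation belongs to one measure.
- In the second item of Section 9.5.1, GSR and high frequency HRV are again joined by *or*, and there the word must mean each, because Sections 3 and 9.1 list them as separate outcomes.
- The outcomes table in Section 9.5 lists GSR and HRV together in one primary-outcome row. That row is an inventory of measurements, so it shows that both are analysed but not how the screen is read.

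On the index-by-index reading, the figures from Step 1 apply to each index exactly as Section 9.2 gives them.

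**The case for a change.** The strongest case for a change is that the ambiguity would often come into play. If nothing is associated and the indices are independent, exactly one passes in about 29% of studies. If both have a true correlation of 0.36, at least one passes in about 94% to 89% of studies for c from 0.3 to 0.7, not 80%. A pilot whose product is a choice of what to study next should say what its criterion applies to, and doing so would cost a sentence.

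Part of this stands. No sentence settles the point, and the arithmetic is right. What does not stand is the consequence. Section 9.2 attaches no go/no-go step, claim or later stage to the screen; it describes what the team would find worth pursuing. It is also not the only benchmark, since the significance test at a true correlation of 0.54 sits beside it. When one index passes and the other does not, the two correlations show which, so a later reader can apply either reading. The 32% is the independence value, and Section 2.2 presents GSR and HRV as products of the same autonomic regulation; positive correlation between the indices would narrow the contrast with 17%. Clustering by provider, with the goal of four providers seeing six subjects each, bears on the size of these rates but says nothing about which reading was meant.

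**Conclusion.** No change is needed. Section 9.2 leaves unsaid how the screen treats two concordance indices, but this is a gap that an analyst fills sensibly: compute both correlations, compare each with 0.20 and report both. On that reading the two 80% figures are correct as they stand.

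The size of the issue is the difference between a 17.4% chance pass rate for one index and 22% to 32% for at least one of two, for assumed inter-correlations of 0.9 down to 0, with independent dyads and normal data. The plan states no null pass rate, so neither value contradicts it. A sentence saying that the criterion applies to each index would be a courtesy to readers. It would leave the data collected, the analyses, the outcome list, the sample size and every reported result as they are, and no multiplicity correction is called for in a pilot screen of this kind.
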